EMPA-KIDNEY Body Composition Measurement Substudy

Study Title: A multicentre international randomized parallel group double-blind placebo-

controlled clinical trial of EMPAgliflozin once daily to assess cardio-renal

outcomes in patients with chronic KIDNEY disease

Sponsor protocol number: 1245-0137

Protocol identifier: CTSUEMPA-KIDNEY1.4 2018-04-25

EudraCT number: 2017-002971-24

Summary

This document provides the rationale and design of an EMPA-KIDNEY substudy to measure body composition in a subset of the 5000 EMPA-KIDNEY participants using bioimpedenace spectroscopy. The substudy does not alter the main protocol in any respect.

Background

In the EMPA-REG OUTCOME trial, empagliflozin 10-25mg was shown to reduce the composite outcome of death from cardiovascular causes, nonfatal myocardial infarction, or nonfatal stroke by 14% compared to placebo (hazard ratio [HR] 0.86, 0.74-0.99) in 7020 people with type 2 diabetes mellitus (T2DM) and prior atherosclerotic cardiovascular disease. This effect was in large part the result of a highly significant 38% (HR 0.62, 0.49-0.77) reduction in cardiovascular death. The prespecified secondary outcome of hospitalization for heart failure was reduced by 35% (HR 0.65, 0.50-0.85). Exploration of EMPA-REG OUTCOME data has suggested that the increase in haematocrit caused by empagliflozin, a possible surrogate for reductions in plasma volume, was the intermediate clinical parameter with the largest mediating effect on the reduction in cardiovascular death. These observations may have particular relevance in people with chronic kidney disease (CKD) who have disturbed salt and water homeostasis which may cause chronic fluid overload which in turn contributes to the observed excess of structural heart disease and heart failure.

In EMPA-REG OUTCOME, allocation to empagliflozin led to a sustained loss of weight (of about 2Kg from a mean of 86Kg) and a 2cm reduction in waist circumference (from a mean of 105cm).¹ How much of this weight change reflected reduction in total body water versus adipose tissue is unknown. A previous trial suggested that, after 2 years, weight loss resulting from SGLT-2 inhibition in people with T2DM appears almost completely attributable to reduced adipose tissue (measured using dual energy X-ray absorptiometry).⁵ Lower kidney function substantially reduces glycosuric effects of SGLT-2 inhibition, and so reduced calorie loss at lower levels of kidney function may

[figure not shown]

attenuate any loss of adipose tissue. However, no attenuation of the weight-lowering effects of SGLT-2 inhibition was identified in those with CKD compared to those without (within the range of kidney function studied to date). Furthermore, meta-analysis of three large placebo-controlled trials suggests effects of SGLT-2 inhibition on heart failure are at least as large among those with reduced kidney function. Part of the preserved effect of SGLT-2 inhibition on body weight and heart failure in CKD may therefore result from reductions in excess extracellular water (ECW) being preserved in those with CKD, despite attenuated effects on glycosuria. This raises a hypothesis that the effects of empagliflozin on excess ECW and fat levels may be different in people with different levels of kidney function.

Figure 1: Effect of SGLT-2 inhibition versus placebo on hospitalization for heart failure, by baseline kidney function (meta-analysis EMPA-REG OUTCOME, CANVAS and DECLARE) 9

Trend across subgroups p=0.03

Bioimpedance spectroscopy can assess different resistance patterns in the body which are affected by the amount of water present. Low frequency current exclusively passes extracellularly, whereas high frequencies can pass through all body water compartments. Comparing spectroscopy readings over a range of frequencies it is possible to derive total body water in Litres and separately the volume of ECW. From such measurements it is also possible to estimate normally hydrated adipose tissue and lean tissue mass, from which an index referred to as "Fluid Overload" (or overhydration) can be algorithmically calculated. Sustained "Fluid Overload" measured by bioimpedance spectroscopy has been associated with increased risk of mortality among people on dialysis, and some dialysis units are now using bioimpedance spectroscopy measurements clinically to guide patients' fluid management and dialysis prescription.

At each Follow-up Visit, EMPA-KIDNEY participants will have their weight measured and central plasma/serum blood samples collected. At Randomization, 2 & 18 months and Final Follow-up Visit, they will also have a measure of waist and hip circumference. A substudy using bioimpedance-

based body composition measurements will ensure uncertainty about the effects of empagliflozin on ECW, adipose tissue and particularly "Fluid Overload" will be assessed in a CKD population.

Aims

The primary aim of this substudy is to use bioimpedance spectroscopy to assess, in a subset of EMPA-KIDNEY participants, the effect of empagliflozin 10mg versus matching placebo on "Fluid Overload" at the 2 month and 18 month Follow-up Visits.

Secondary aims are to use bioimpedance spectroscopy to assess:

- 1. Whether any effects of empagliflozin 10mg versus matching placebo on "Fluid Overload" are modified by baseline factors, in particular by level of kidney function, glycosylated haemoglobin, body mass index, NT-proBNP, age, sex, RAS inhibitor use, and different diuretics
- 2. The effects of empagliflozin 10mg versus matching placebo early and later during follow-up on:
 - o ECW
 - Intracellular water (ICW)
 - Adipose tissue mass indexed to weight (i.e. %)
 - Lean tissue mass indexed to weight (i.e. %)

Exploratory aims are to:

 Assess if changes in ECW, ICW, % adipose tissue mass, % lean tissue mass and "Fluid Overload" correlate with changes in blood pressure and relevant other biomarkers.

Sample size estimates

The study will start a vanguard phase in a small number of sites in which bioimpedance spectroscopy will be performed at Randomization, 2 months and 18 months of Follow-up Visits. This vanguard phase will be expanded to other sites once feasiblity of adding a bioimpedance spectroscopy measurement is demonstrated. Feasiblity will be based on feedback from the participating sites, successful completion of the other protocol-specified procedures and logistical considerations. It is estimated that at least 400 (of the 5000) EMPA-KIDNEY participants with follow-up bioimpedance spectroscopy measurements will provide ample power (>90%, 2p=0.05) to detect at least a ±300mL difference in "Fluid Overload" (reference range in healthy adults is ± 1100mL with a standard deviation of 900mL) based on an independent 2-sided t-test (Table 1).

Table 1: Sample size calculations for a study with Randomization Visit measurements

Outcome	Effect size	Standard deviation	Required sample size
"Fluid Overload" (ref range: ±1.1L)	±300mL	900mL	382

Note: An estimate of the correlation between successive bioimpedance spectroscopy measurements would be required to calculate the reduction in sample size that could be achieved by using ANCOVA analyses, but no such longitudinal data has yet been collected in a CKD population.

If a bioimpedance spectroscopy measurement at the Randomization Visit is shown to be infeasible, the substudy will be modifed to exclude the measurement at the Randomization Visit and only be performed at the relatively less busy phases of the study (i.e. measurements will be restricted to the 2 and 18 month Follow-up Visits). In this design, the sample size would need to increase to 850. This is because the absence of a bioimpedance spectroscopy measurement at the Randomization Visit means any imbalances in "Fluid Overload" between treatment arms at baseline cannot be corrected for. These imbalances could result in either the treatment effect being overestimated or a smaller than expected difference in mean "Fluid Overload" at follow-up. However, with a sample size of 850, the probability of large baseline imbalances is small, making it unlikely that the treatment effect would be overstated by more than 100mL (Table 2). With a sample size of 850, there would be sufficient power to detect a reduced difference in mean "Fluid Overload" of ± 200 mL at follow-up. This calculation is based on an independent 2-sided t-test using data from a healthy population (Note: sample size estimates differ little if dialysis population data are used).

[figure not shown]
Table 2: Sample size calculations for a study without Randomization Visit measurements

Sample size	Assumed possible baseline imbalance in Fluid Overload (mL)	Probability of a baseline imbalance at least this size due to chance (1-sided)	Difference between groups at follow-up (mL) after subtracting possible baseline imbalance from assumed treatment effect of 300 mL	Power to detect reduced difference in follow-up values at 2p=0.05
850				
	0	Not applicable	300	>99%
	50	12.6%	250	98%
	100	1.1%	200	90%
	150	0.03%	150	68%
	200	0.0002%	100	37%

Data Analysis Plan

The primary analysis will estimate the differences in "Fluid Overload" between treatment groups across all time points, regardless of whether a participant received all, some or none of their allocated treatment (i.e. intention-to-treat analyses). Secondary outcomes include ECW, ICW, % adipose tissue mass, and % lean tissue mass". Differences in "Fluid Overload" and the secondary outcomes between treatment groups overall, and separately at 2 and 18 months, will be calculated using linear regression adjusted (or stratified) for the elements included in the minimization

algorithm. The primary analysis will focus on a weighted average of the values at the two time points (with weights proportional to the amount of time between visits). Missing measurements will be imputed. Results from the imputed analyses will be compared with those from equivalent "complete-case" analyses, but primary emphasis will be placed on the results after multiple imputation. More complete details of statistical methods, including definitions of subgroups, methods of imputation, approaches to adjustments and weighting of averages will be set out in a separate full Data Analysis Plan which will be consistent with the main study Data Analysis Plan.

Flowchart of Substudy Activities

INVITATION

- Invite potential participants shortly before or at the time of the Randomization Visit
- Written informed consent is sought from willing individuals at the first visit when a bioimpedance spectroscopy measurement is offered

RANDOMIZATION VISIT AND AT 2 & 18 MONTHS OF FOLLOW-UP

 A bioimpedance spectroscopy measurement is added to the protocol-specified study follow-up visit procedures

Design

Eligibility: In selected regions, EMPA-KIDNEY Local Clinical Centres (LCCs) with a Fresenius Medical Care Body Composition Monitor (BCM) machine will be invited to join this optional substudy. All those participants at these LCCs who have yet to attend the relevant scheduled study visit are eligible for invitation. There are no exclusion criteria.

Invitation and methods: Potential participants will be invited to join this substudy at before or around the time of their Randomization Visit. At the relevant visit, clinic staff will explain the substudy to potential participants using the Participant Information Leaflet and Consent Form. Consenting participants will have a measure of bioimpedance made in addition to the protocol-specified follow-up procedures. Bioimpedance measurements take about 2 minutes to record and pose no risk to health (although it is conceivable the 4 self-adhesive pads could rarely cause a skin reaction).

Body Composition Measurement

Training materials on how to perform Body Composition Measurements will be provided. The measurement requires

EMPA-KIDNEY Body composition measurement substudy justifi V1.0 – 02-MAR-2019

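### The fallback size of 850 does not follow from losing the baseline measurement: 382 already uses no baseline, Table 2 counts baseline variation twice, and its imbalance probabilities are too small

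*Protocol*

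**What the plan says.** All of this is in the protocol's section on sample size estimates.

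- **Main design.** The target is a 300 mL difference in Fluid Overload with SD 900 mL, two-sided 0.05 and power above 90%. Table 1 gives 382, and the text rounds this up to at least 400. The calculation is "based on an independent 2-sided t-test (Table 1"). The table is headed "Table 1: Sample size calculations for a study with Randomization Visit measurements", yet its note says that a correlation estimate would be needed to "calculate the reduction in sample size that could be achieved by using ANCOVA analyses", and that none exists in CKD.
- **Fallback design.** If the baseline measurement is infeasible, "In this design, the sample size would need to increase to 850". The text argues that uncorrected imbalance could either inflate the effect or shrink the observed difference. It says that 850 makes large imbalances improbable, "making it unlikely that the treatment effect would be overstated by more than 100mL", and leaves enough power for a difference reduced to 200 mL.
- **Table 2 (N = 850).** One column is headed "Probability of a baseline imbalance at least this size due to chance (1-sided"): 12.6%, 1.1%, 0.03% and 0.0002% for 50, 100, 150 and 200 mL. Another gives the difference "after subtracting possible baseline imbalance from assumed treatment effect of 300 mL". The last gives power for that remainder: >99%, 98%, 90%, 68% and 37% for 300, 250, 200, 150 and 100 mL.

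**The concern.** A calculation that never used a baseline value cannot need more participants when the baseline value is dropped. Measuring baseline could only bring the number below 382. Yet the protocol treats 382 as the size with baseline and more than doubles it without.

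The step from one to the other looks like a double count. Under randomization, chance imbalance at baseline is part of the sampling variation of the follow-up means, and the 900 mL SD already covers it. Table 2 takes the imbalance off the effect and then charges the full SD again.

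The other stated ground, limiting overstatement of the effect, does depend on N. It is a precision aim, however, and the probabilities that support it look too small for a difference between two arms of 425.

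If the fallback were used, the protocol would present more than twice the participants as a need when it is a choice, and would understate the risk that might justify that choice.

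**Working it through.** **Inputs.** Effect 300 mL, SD 900 mL, two-sided 0.05, power 90%, independent t-test, N = 382, 400 and 850 (all from the protocol). Allocation 1:1 is an assumption; it reproduces 382 and every Table 2 power.

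**1. The plan's sizes and powers.** Normal approximation: N = 4 × (1.96 + 1.2816)² × (900/300)² = 378.3, or 380 in two equal arms of whole participants. The exact t-test needs 380.2, hence 382. For 200 mL the normal formula gives 852 and the exact t-test 853.0.

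| N | True difference | t-test power | Protocol |
|---|---|---|---|
| 382 | 300 mL | 90.1% | >90% claimed for at least 400 |
| 400 | 300 mL | 91.4% | >90% |
| 850 | 300 mL | 99.8% | >99% |
| 850 | 250 mL | 98.1% | 98% |
| 850 | 200 mL | 89.9% | 90% |
| 850 | 150 mL | 68.0% | 68% |
| 850 | 100 mL | 36.6% | 37% |

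The sizes and powers reproduce without any baseline term. So 850 is the size for a true 200 mL difference, and 382 is the size for 300 mL with no baseline adjustment.

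**2. Does lack of baseline cost power at 300 mL?** Follow-up-only t-tests were simulated at N = 382 with baseline–follow-up correlations of 0.3, 0.5, 0.7 and 0.9 (assumed range). Power was 90.5%, 90.5%, 90.1% and 89.9%. It does not depend on the correlation.

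**3. The double count.** At N = 850 the SE of the difference between arms is 900 × √(4/850) = 61.7 mL. Given an adverse baseline imbalance b and correlation rho, and equal SD at both visits, the follow-up difference has mean 300 − rho × b and SD 61.7 × √(1 − rho²). Only part of b carries over, and the remaining spread is smaller than 61.7 mL. The significance threshold is about 1.963 × 61.7 = 121.2 mL.

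- b = 100 mL: the lowest power over rho from 0 to 0.999 is at rho = 0.56: Φ((244 − 121.2)/(61.7 × 0.828)) = Φ(2.40) = 99.2%. Table 2 shows 90%.
- b = 200 mL: 93% at rho 0.5, 69% at 0.8 and 28% at 0.95. Table 2 shows 37%.

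A valid conditional power, averaged over the chance distribution of b, must return the unconditional power. The calculation above does: about 90% at N = 382 and 99.8% at N = 850. Table 2's method averages to Φ((300/SE − 1.96)/√2). At N = 382 (SE 92.1 mL) this is Φ(0.917) = 82.0%, against a true 90.1%. At N = 850 it is Φ(2.05) = 98.0%, against 99.8%.

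**4. Imbalance probabilities at N = 850.** These are one-sided P(Z > b/SE).

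| b | Table 2 | SE of one arm's mean, 900/√425 = 43.7 mL | SE of the difference, 61.7 mL |
|---|---|---|---|
| 50 mL | 12.6% | 12.6% | 20.9% |
| 100 mL | 1.1% | 1.10% | 5.3% |
| 150 mL | 0.03% | 0.030% | 0.76% |
| 200 mL | 0.0002% | 0.0002% | 0.06% |

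The printed column matches one arm's SE in all four rows. Reading 850 as per arm would also give 43.7 mL, but power at 200 mL would then be 99.6%, not 90%. The two columns therefore cannot come from one design.

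**5. N and overstatement.** The probability of 100 mL or more is 13.9% at N = 382, 13.3% at 400 and 5.3% at 850. The printed 1.1% would need 4 × (900 × 2.29/100)², about 1,700 participants.

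**The case against.** **The protocol does not literally claim that 850 is needed for 90% power at 300 mL.** Table 2 shows above 99% there, and 90% is claimed only for the reduced 200 mL. That is so, and 850 is correct for a true 200 mL difference. But the protocol says the number must rise because imbalance cannot be corrected, and it obtains 200 mL by subtracting imbalance from an unchanged 300 mL effect. That reasoning fails.

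**The Table 1 note already tells the reader that no credit for baseline was taken.** This stands, and it is why relabelling Table 1 is a small change. The note also makes the jump to 850 harder to defend.

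**Only rho times the imbalance carries over to follow-up, so 5.3% overstates the risk due to baseline alone.** The chance that the carry-over exceeds 100 mL at N = 850 is 0.06% at rho 0.5, 1.0% at 0.7, 2.1% at 0.8 and 3.6% at 0.9. This is correct for that component. The column, however, is labelled as the imbalance itself, for which 5.3% is right. Total chance overstatement of more than 100 mL at follow-up is also 5.3% at any rho, on Table 2's unadjusted basis.

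**The trial uses minimization and adjusts for its elements, which may reduce the imbalance.** If those elements explained 20% or 30% of the variance (assumed values), the probability at 100 mL would be 3.5% or 2.6%. This is a fair caveat. The corrected figures should be labelled as unadjusted.

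**Table 2 is not pessimistic in every row.** This is true for a 200 mL imbalance with high correlation (28% against 37%). It does not validate the method.

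**Conclusion.** The concern holds. Loss of the baseline measurement does not raise the size needed for 90% power at a true 300 mL effect: 382 is already that size. Table 2's subtraction counts chance baseline variation twice, and its probabilities use the wrong standard error, understating the risk at 100 mL about fivefold (5.3/1.1 = 4.8).

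The consequence is limited. The error is conservative for power, applies only if the fallback is used, and leaves the main design of at least 400 untouched. A sponsor may reasonably prefer 850 for precision: the 95% half-width is about 121 mL, against 176 mL at 400.

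The figures assume SD 900 mL, 1:1 allocation and no covariate adjustment. The conditional powers also assume equal SD at baseline and follow-up, with the correlation unknown.

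**What to change.** 1. Retitle Table 1 as the size without baseline adjustment, conservative if baseline is measured.
2. Restate 850 as a sponsor's choice that gives 90% power for a true 200 mL difference and limits chance overstatement, not as a requirement created by the missing baseline.
3. Correct Table 2's probabilities to 20.9%, 5.3%, 0.76% and 0.06%, marked as unadjusted. Delete the subtracted-difference and reduced-power columns. If the powers are kept, present them only as power against true differences of 300 to 100 mL.
4. Describe the gain from baseline as an ANCOVA reduction, with N multiplied by roughly 1 − rho² for a single follow-up value. With rho unknown in CKD, no exact figure should be given; illustratively, 380 falls to 346, 284 or 194 at rho 0.3, 0.5 or 0.7.

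The cost is wording and one table. No participants are added, and the main design does not change.

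### Fallback design: baseline imbalance in Fluid Overload can be partly corrected through baseline covariates, and naming only the minimization elements risks lost precision, mainly for ECW and ICW

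*Protocol*

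**What the plan says.** The fallback is described under Sample size estimates. Without a bioimpedance measurement at the Randomization Visit, imbalances "between treatment arms at baseline cannot be corrected for". This is the stated reason for a larger study: "In this design, the sample size would need to increase to 850". The calculation is an unadjusted two-sample t-test with the healthy-adult SD ("reference range in healthy adults is ± 1100mL with a standard deviation of 900mL").

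The Data Analysis Plan section names one covariate set for all outcomes: "linear regression adjusted (or stratified) for the elements included in the minimization" algorithm. The document does not list those elements. The same section leaves approaches to adjustment to a separate, fuller Data Analysis Plan.

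Other sections show what else is known at baseline. The Background says of the main trial's participants, at Randomization among other visits, that "they will also have a measure of waist and hip circumference". Secondary aim 1 lists as baseline factors, besides kidney function and glycosylated haemoglobin, "body mass index, NT-proBNP, age, sex, RAS inhibitor use, and different diuretics". They appear there only as possible effect modifiers. Among the secondary outcomes, adipose and lean tissue mass are expressed as a percentage of weight. ECW and ICW are not indexed to anything.

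**The concern.** Two separate ideas are merged in the fallback rationale. Not having a participant's own baseline Fluid Overload means that it cannot be a covariate. It does not follow that imbalance is beyond correction. Any pre-randomization variable that predicts Fluid Overload removes part of the chance difference between arms when it enters the regression. The planned adjustment for minimization elements already does this to whatever extent those elements are predictive, so the rationale is at odds with the protocol's own analysis.

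The second issue is precision. ECW and ICW are volumes and can be expected to vary with body size. If size is left out of the model, differences in size between people go into the error term. Size is dealt with for adipose and lean mass by indexing, but for the two water volumes only if the unlisted minimization elements happen to carry it. A fuller analysis plan written from the premise that nothing can be corrected has little prompt to add these covariates.

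**Working it through.** **Inputs from the protocol.** N = 850; SD of Fluid Overload 900 mL; assumed effect 300 mL; reduced difference 200 mL; two-sided 5% level. Allocation is taken as 1:1 (425 per arm), an assumption because this document gives no ratio.

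**Reproducing the stated power.** SE = 900 × √(2/425) = 61.7 mL. Power = Φ(difference/SE − 1.96).
- 200 mL: 200/61.7 − 1.96 = 1.28, power 90.0% (Table 2: 90%).
- 300 mL: power 99.8% (Table 2: >99%).
- 250, 150 and 100 mL: 98.2%, 68.1% and 36.7% (Table 2: 98%, 68%, 37%).

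The power column reproduces throughout. N for 90% power at 200 mL is 852 by the normal formula, against the stated 850.

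**Fluid Overload with baseline covariates.** Residual SD = 900 × √(1 − R²), where R² is the share of variance explained beyond the minimization elements. The document gives no R², so a range is assumed. It is kept low because Fluid Overload is derived relative to normally hydrated tissue, so body size may explain less of it.

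| Assumed R² | Residual SD (mL) | SE at N=850 (mL) | Power for 200 mL | N for 90% power at 200 mL |
|---|---|---|---|---|
| 0 | 900 | 61.7 | 90.0% | 852 |
| 0.05 | 877 | 60.2 | 91.4% | 810 |
| 0.10 | 854 | 58.6 | 92.7% | 766 |
| 0.20 | 805 | 55.2 | 95.2% | 682 |
| 0.30 | 753 | 51.7 | 97.2% | 596 |

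**ECW and ICW.** The document gives neither an SD nor a target difference for these, so the result is expressed relative to the SD. The SE is multiplied by √(1 − R²). The difference detectable with 90% power is (1.960 + 1.282) × √(2/425) × √(1 − R²) SD units.

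| Assumed R² | Reduction in SE | Detectable difference (SD units) |
|---|---|---|
| 0 | – | 0.222 |
| 0.50 | 29% | 0.157 |
| 0.70 | 45% | 0.122 |

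Both tables overstate the gain if the minimization elements already explain part of the same variance.

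**A separate matter.** The imbalance probabilities in Table 2 do not reproduce at 425 per arm. For 100 mL, 1 − Φ(100/61.7) = 5.3%, against 1.1% stated; the printed values match 850 per arm (SE 43.7 mL). That is a distinct error, and nothing here rests on it.

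**The case against.** The strongest reply is that the covariate list is not closed. The Data Analysis Plan section defers approaches to adjustment to a separate document, and a full covariate list for a contingency design is commonly left there. This stands: lost precision is a risk, not an established consequence. It does not cover the statement that imbalance is uncorrectable, which is made in this document and used to justify 850.

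A second reply is that, in context, the sentence only contrasts having a participant's own baseline value with not having it, and that the error is on the cautious side because it raises N. That is a fair reading of the intent. As worded, though, the sentence says more than that.

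Third, the fallback may never be used, since it applies only if the Randomization measurement proves infeasible. This also stands and limits the weight of the point.

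A reader might infer two stronger conclusions, and the document supports neither. One is that the fallback is underpowered for its primary outcome. It is not: with no covariates, power is 99.8% for 300 mL and 90% for 200 mL. The t-test's standard error also already includes chance baseline imbalance, so subtracting an imbalance from the effect counts it twice. The other is that unadjusted ECW and ICW comparisons would be too imprecise to show the shift the substudy targets. The protocol sets a target only for Fluid Overload. Applying 300 mL to ECW or ICW borrows a figure, and any result in litres would also need an SD that the document does not give.

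**Conclusion.** The point holds in a limited form. The statement that baseline imbalance cannot be corrected is too absolute: the participant's own value is unavailable, but partial correction is possible with variables the document itself names. With only the minimization elements named, precision may be lost, and the loss is likely to be greatest for ECW and ICW. That ranking is reasoned from their being unindexed volumes; it is not documented.

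For Fluid Overload the gain is modest, from 90% to 91–97% power for 200 mL. For ECW and ICW the standard error could fall by 29–45%. Both figures rest on assumed R² values and 1:1 allocation, and shrink if the minimization elements already carry this variance. No stated power claim fails, so this is an inexpensive improvement in precision for a design that may not be needed.

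**What to change.** Under Sample size estimates, say that without a Randomization measurement imbalance *can only be partly corrected for*.

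In the Data Analysis Plan section, or in the separate plan it refers to, state that in the fallback the regressions also adjust for prespecified baseline body size (BMI or weight and height, and waist and hip circumference), sex, log NT-proBNP and diuretic use. Body size and sex should always be in the models for ECW and ICW. Fix the set before unblinding, and handle missing covariate values within the multiple imputation already planned, so that covariates and outcomes are treated consistently.

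The cost is wording and a few degrees of freedom out of 850. No new measurement is needed, because waist and hip circumference are already taken at Randomization and the other variables are baseline factors on which secondary aim 1 already relies.

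### Table 2 understates the chance of baseline imbalance: with 850 participants in total, the one-sided chance of a 100 mL imbalance is 5.3%, not 1.1%

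*Protocol*

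**What the plan says.** The section on sample size estimates in the Protocol plans for measurements at randomization, 2 months and 18 months. It also sets out a fallback: "If a bioimpedance spectroscopy measurement at the Randomization Visit is shown to be infeasible", only the two follow-up measurements are made. For that case, "In this design, the sample size would need to increase to 850", because an imbalance in Fluid Overload at baseline could then not be corrected for.

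The protocol reassures the reader that with this number large imbalances are improbable, "making it unlikely that the treatment effect would be overstated by more than 100mL (Table 2"). Table 2 has a column headed "Probability of a baseline imbalance at least this size due to chance (1-sided"), with entries of 12.6%, 1.1%, 0.03% and 0.0002% for 50, 100, 150 and 200 mL. Beside it stands the power to detect what remains of a 300 mL effect after the imbalance is subtracted: >99%, 98%, 90%, 68% and 37% for remaining differences of 300, 250, 200, 150 and 100 mL.

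The only SD given is in the same section: "reference range in healthy adults is ± 1100mL with a standard deviation of 900mL".

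**The concern.** Both columns of Table 2 describe the sampling variability of the same quantity, a difference between two arm means of Fluid Overload, at the same sample size and with the same SD. They must therefore share one standard error, and they do not.

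The imbalance column is the only numerical support for the claim that leaving out the baseline measurement carries little risk of an overstated effect. If its standard error is too small, anyone deciding whether the Randomization Visit measurement can be dropped sees too small a risk. The row that matters most is 100 mL, because the reassuring sentence names that size.

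**Working it through.** **Inputs.** Total sample size 850 (text and Table 2). SD 900 mL (text and Table 1). Two-sided alpha 0.05 for power, one-sided probabilities for imbalance (Table 2 headings). Independent two-sample t-test (text). Allocation 1:1 is an assumption, as the document gives no ratio.

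**Step 1: the sample sizes are totals.** The text counts "It is estimated that at least 400 (of the 5000) EMPA-KIDNEY participants with follow-up bioimpedance spectroscopy measurements". Table 1 agrees: t-test power for 300 mL at SD 900 mL is 90.1% with 191 per arm (382 in total), but would be 99.6% with 382 per arm.

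**Step 2: reproduce the power column.** With 425 per arm,

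SE = 900 × √(2/425) = 61.74 mL.

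| Difference (mL) | Printed power | 425 per arm | 850 per arm |
|---|---|---|---|
| 300 | >99% | 99.8% | 100% |
| 250 | 98% | 98.1% | 100% |
| 200 | 90% | 89.9% | 99.6% |
| 150 | 68% | 68.0% | 93.0% |
| 100 | 37% | 36.6% | 62.9% |

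The printed column rests on 850 in total and an SE of 61.74 mL.

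**Step 3: compute the imbalance column with the same SE.** The one-sided probability of an imbalance of at least d is 1 − Φ(d/SE).

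| d (mL) | Printed | SE 61.74 mL | SE 43.66 mL |
|---|---|---|---|
| 50 | 12.6% | 20.9% | 12.60% |
| 100 | 1.1% | 5.26% | 1.10% |
| 150 | 0.03% | 0.756% | 0.0295% |
| 200 | 0.0002% | 0.0599% | 0.00023% |

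Using the t distribution instead of the normal hardly changes this (5.28% at 100 mL).

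**Step 4: find the SE behind the printed cells.** Inverting each cell and allowing for rounding gives these ranges:

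- 50 mL: 43.56 to 43.74
- 100 mL: 43.33 to 43.99
- 150 mL: 43.09 to 44.25
- 200 mL: 42.82 to 43.81

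The range common to all four is 43.56 to 43.74 mL. It contains 61.74/√2 = 43.66 mL. That value equals 900 × √(2/850), as if there were 850 per arm, and also 900/√425, the SE of a single arm's mean. The document does not show which was used.

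**Step 5: try other readings.**

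- Two-sided probabilities move further from print (10.5% at 100 mL), and the heading says one-sided.
- Unequal allocation only enlarges the SE; a 2:1 split of 850 gives 65.5 mL.
- An SD of 636 mL would give the printed probabilities at 425 per arm, but power at 200 mL would then be 99.6% rather than the printed 90%, and the stated SD is 900 mL.
- An SD of 1100/1.96 = 561 mL, read from the reference range, fits neither column.

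**Step 6: size of the discrepancy.** At 100 mL, 5.26/1.10 = 4.8. The imbalance that does carry a 1.1% one-sided chance is 2.290 × 61.74 = 141 mL, nearly half of the 300 mL target.

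**The case against.** No reading rescues the four printed cells, so the case on the other side is about weight and wording.

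First, the reassuring sentence contains no probability, and a 5.3% one-sided chance can still be called unlikely. The sentence is weakened rather than reversed. This stands.

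Second, nothing in the design depends on the column. The figure of 850 corresponds to 90% power at 200 mL, which reproduces, and the fallback may never be used. This also stands and limits the scope, but the column remains the only figure offered in support of the reassurance.

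Third, a baseline imbalance need not carry over in full to follow-up. With equal SDs the expected carry-over is ρ times the imbalance, where ρ is the correlation between baseline and follow-up. The note to Table 1 says no longitudinal data in CKD yet exist from which to estimate it. Over an assumed range, the chance of a carry-over of at least 100 mL, 1 − Φ(100/(ρ × 61.74)), is 5.3% at ρ = 1.0, 3.6% at 0.9, 2.1% at 0.8, 1.0% at 0.7 and 0.06% at 0.5. So 5.3% is a worst case for overstatement of the effect. It does not defend the printed cells, because their heading concerns the baseline imbalance itself and the table subtracts that imbalance mL for mL. It does mean a corrected sentence should speak of the imbalance, or state the full carry-over assumption.

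Fourth, the Data Analysis Plan section refers to a minimization algorithm and adjusts for its elements, which would reduce imbalance to the extent that they predict Fluid Overload. The document does not allow that to be sized. It is not an input to Table 2, and to explain the printed values it would have to remove exactly half the variance in one column and none in the other.

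**Conclusion.** The concern holds. Under the table's own inputs (850 in total, SD 900 mL) and an assumed 1:1 allocation, the imbalance probabilities are 20.9%, 5.3%, 0.76% and 0.06%. Any other allocation ratio would make them larger. The 100 mL risk is about 1 in 19 against a printed 1 in 91, and the 50 mL risk about 1 in 5 against 1 in 8. The last two rows are understated about 25-fold and 260-fold (unrounded values), though they remain below 1% either way.

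This is an arithmetic error in the justification of the fallback design and should be fixed. It does not touch the sample size of 850, the power column, the planned analysis or the main design with a baseline measurement.

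**What to change.** In Table 2, replace the four probabilities with 20.9%, 5.3%, 0.76% and 0.06%. Add a note giving the basis: 425 per arm, SD 900 mL, SE 61.7 mL, with imbalance assumed to carry over in full to follow-up.

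Reword the supporting sentence to say that, with 850 participants in total, there is about a 5% (1 in 19) chance of a baseline imbalance of at least 100 mL in the direction that would overstate the effect.

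Leave the sample size of 850 and the power column as they are. The cost is four cells, one note and one sentence, with no operational or analysis change.
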